14.3.1.2 Unsolicited Adverse Events

Table 45: Summary of Unsolicited Adverse Events by Study Group, MedDRA System Organ Class and Preferred Term – Safety Population

[Implementation Note: SOC and PT will be sorted by number of subjects. Any SOC that is in either group should be presented (i.e. if SOC1 has 1 event in M2SR but 0 in placebo, SOC1 will still be shown for placebo). For any SOC with a single PT the “Any PT” row will be omitted.]

Study Arm	MedDRA System Organ Class	MedDRA Preferred Term	Day 1-7 Post Vaccination (N=X)				Day 8-21 Post Vaccination (N=X)				Any Time Post Vaccination (N=X)			
			n	%	95% CI	Events	n	%	95% CI	Events	n	%	95% CI	Events
M2SR (N=X)	Any SOC	Any PT	x	xx	xx, xx	x	x	xx	xx, xx	x	x	xx	xx, xx	x
	[SOC 1]	Any PT												
		[PT 1]												
		[PT 2]												
	[SOC 2]	Any PT												
		[PT 1]												
		[PT 2]												
Placebo (N=X)	Any SOC	Any PT	x	xx	xx, xx	x	x	xx	xx, xx	x	x	xx	xx, xx	x
	[SOC 1]	Any PT												
		[PT 1]												
		[PT 2]												
	[SOC 2]	Any PT												
		[PT 1]												
		[PT 2]												

Note: N = number of subjects in the Safety Population. This table presents number and percentage of subjects. A subject is only counted once per PT/time point.

Table 46: Unsolicited Adverse Events by MedDRA System Organ Class and Preferred Term, Maximum Severity, Relationship, and Study Group – Safety Population

[Implementation Note: SOC and PT will be sorted by the total number of subjects (any severity, any relationship, descending).]

MedDRA System Organ Class	Preferred Term	Severity	M2SR (N = X)						Placebo (N = X)						All Subjects (N = X)							
			Related		Not Related		Total		Related		Not Related		Total		Related		Not Related		Total			
			n	%	n	%	n	%	n	%	n	%	n	%	n	%	n	%	n	%		
Any SOC	Any PT	Any Severity	x	xx	x	xx	x	xx	x	xx	x	xx	x	xx	x	xx	x	xx	x	xx	x	xx
		Mild	x	xx	x	xx	x	xx	x	xx	x	xx	x	xx	x	xx	x	xx	x	xx	x	xx
		Moderate	x	xx	x	xx	x	xx	x	xx	x	xx	x	xx	x	xx	x	xx	x	xx	x	xx
		Severe	x	xx	x	xx	x	xx	x	xx	x	xx	x	xx	x	xx	x	xx	x	xx	x	xx
SOC 1	PT 1	Any Severity	x	xx	x	xx	x	xx	x	xx	x	xx	x	xx	x	xx	x	xx	x	xx	x	xx
		Mild	x	xx	x	xx	x	xx	x	xx	x	xx	x	xx	x	xx	x	xx	x	xx	x	xx
		Moderate	x	xx	x	xx	x	xx	x	xx	x	xx	x	xx	x	xx	x	xx	x	xx	x	xx
		Severe	x	xx	x	xx	x	xx	x	xx	x	xx	x	xx	x	xx	x	xx	x	xx	x	xx
	PT 2	Any Severity	x	xx	x	xx	x	xx	x	xx	x	xx	x	xx	x	xx	x	xx	x	xx	x	xx
		Mild	x	xx	x	xx	x	xx	x	xx	x	xx	x	xx	x	xx	x	xx	x	xx	x	xx
		Moderate	x	xx	x	xx	x	xx	x	xx	x	xx	x	xx	x	xx	x	xx	x	xx	x	xx
		Severe	x	xx	x	xx	x	xx	x	xx	x	xx	x	xx	x	xx	x	xx	x	xx	x	xx

Note: N = Number of subjects in the Safety Population.

Table 47: Summary of Related Unsolicited Adverse Events by Study Group and MedDRA System Organ Class and Preferred Term – Safety Population

[Implementation Note: SOC and PT will be sorted by number of subjects. Any SOC that is in either group should be presented (i.e. if SOC1 has 1 event in M2SR but 0 in placebo, SOC1 will still be shown for placebo). For any SOC with a single PT the “Any PT” row will be omitted.]

Study Group	MedDRA System Organ Class	MedDRA Preferred Term	Day 1-7 Post Vaccination (N=X)				Day 8-21 Post Vaccination (N=X)				Any Time Post Vaccination (N=X)			
			n	%	95% CI	Events	n	%	95% CI	Events	n	%	95% CI	Events
M2SR (N=X)	Any SOC	Any PT	x	xx	xx, xx	x	x	xx	xx, xx	x	x	xx	xx, xx	x
	[SOC 1]	Any PT												
		[PT 1]												
		[PT 2]												
	[SOC 2]	Any PT												
		[PT 1]												
		[PT 2]												
Placebo (N=X)	Any SOC	Any PT	x	xx	xx, xx	x	x	xx	xx, xx	x	x	xx	xx, xx	x
	[SOC 1]	Any PT												
		[PT 1]												
		[PT 2]												
	[SOC 2]	Any PT												
		[PT 1]												
		[PT 2]												

Note: N = number of subjects in the Safety Population. This table presents number and percentage of subjects. A subject is only counted once per PT/time point.

14.3.2 Listing of Deaths, Other Serious and Significant Adverse Events

Table 48: Listing of Serious Adverse Events - Safety Population*

Adverse Event	No. of Days Post Associated Dose (Duration)	No. of Days Post Dose the Event Became Serious	Reason Reported as an SAE	Severity	Relationship to Study Treatment	If Not Related, Alternative Etiology	Action Taken with Study Treatment	Subject Discontinued Due to AE	Outcome	AESI? NOCMC?	MedDRA System Organ Class	MedDRA Preferred Term
Subject ID: , Study Group: , AE Number: ,Associated with Dose No.:												
Comments:												
Subject ID: , Study Group: , AE Number: ,Associated with Dose No.:												
Comments:												

Table 49: Listing of Non-Serious, Unsolicited, Moderate or Severe Adverse Events – Safety Population

Adverse Event	No. of Days Post Associated Dose (Duration)	Severity	Relationship to Study Treatment	If Not Related, Alternative Etiology	Action Taken with Study Treatment	Subject Discontinued Due to AE	AESI? NOCMC?	Outcome	MedDRA System Organ Class	MedDRA Preferred Term
Subject ID: , Study Group: , AE Number: ,Associated with Dose No:										
Comments:										
Subject ID: , Study Group: , AE Number: ,Associated with Dose No:										
Comments:										

Table 50: Listing of Adverse Events of Special Interest – Safety Population*

Adverse Event	Vaccination Received at Time of Event?	No. of Days Post Vaccination	Duration of Event	Severity	MedDRA System Organ Class	NOCMC?	Relationship	Outcome
Subject ID: , Study Group: , AE Number:								
Comments:								
Subject ID: , Study Group: , AE Number:								
Comments:								

Table 51: Listing of New Onset Chronic Medical Conditions – Safety Population*

Adverse Event	Vaccination Received at Time of Event?	No. of Days Post Vaccination	Duration of Event	Severity	MedDRA System Organ Class	AESI?	Relationship	Outcome
Subject ID: , Study Group: , AE Number:								
Comments:								
Subject ID: , Study Group: , AE Number:								
Comments:								

14.3.3 Narratives of Deaths, Other Serious and Significant Adverse Events

(not included in SAP, but this is a placeholder for the CSR)

14.3.4 Abnormal Laboratory Value Listings (by Subject)

Table 52: Listing of Abnormal Chemistry Laboratory Results - Safety Population

Subject ID	Study Group	Sex	Age (years)	Planned Time Point	Actual Study Day	Laboratory Parameter (Units)	Result (Severity)	Relationship to Treatment	If Not Related, Alternate Etiology	Action Taken with Study Treatment	Subject Discontinued Due to Result?

Table with similar format:

Table 53: Listing of Abnormal Chemistry Laboratory Results - Safety Population

14.3.5 Displays of Laboratory Results

14.3.5.1 Chemistry Results

Table 54: Laboratory Results by Parameter, Maximum Severity, Time Point, and Study Group – Any Chemistry Parameter

Time Point	Study Group	N	None		Mild / Grade 1		Moderate/ Grade 2		Severe/ Grade 3		Missing	
			n	%	n	%	n	%	n	%	n	%
Screening	M2SR	x	x	xx	x	xx	x	xx	x	xx	x	xx
	Placebo											
Day 8	M2SR											
	Placebo											
Max Severity Post Baseline	M2SR											
	Placebo											

Note: The “Max Post Baseline” rows indicate the maximum severity experienced by each subject at any time point post baseline, including unscheduled assessments.
N= Number of subjects in the Safety Population

Tables with similar format:

Table 55: Laboratory Results by Parameter, Maximum Severity, Time Point, and Study Group – Alanine Aminotransferase

Table 56: Laboratory Results by Parameter, Maximum Severity, Time Point, and Study Group – Aspartate Aminotransferase

Table 57: Laboratory Results by Parameter, Maximum Severity, Time Point, and Study Group – Creatinine

Table 58: Abnormal Laboratory Results Related to Study Treatment by Parameter, Maximum Severity, Time Point, Study Group, and Chemistry Parameter – Safety Population

Laboratory Parameter	Time Point	Treatment Group	N	Mild/ Grade 1		Moderate/ Grade 2		Severe/ Grade 3	
				n	%	n	%	n	%
Any Chemistry Parameter	Day 8	M2SR	x	x	xx	x	xx	x	xx
		Placebo	x	x	xx	x	xx	x	xx
	Max Severity Post Baseline	M2SR	x	x	xx	x	xx	x	xx
		Placebo	x	x	xx	x	xx	x	xx
Alanine Aminotransferase	Day 8	M2SR	x	x	xx	x	xx	x	xx
		Placebo	x	x	xx	x	xx	x	xx
	Max Severity Post Baseline	M2SR	x	x	xx	x	xx	x	xx
		Placebo	x	x	xx	x	xx	x	xx
Aspartate Aminotransferase	Day 8	M2SR	x	x	xx	x	xx	x	xx
		Placebo	x	x	xx	x	xx	x	xx
	Max Severity Post Baseline	M2SR	x	x	xx	x	xx	x	xx
		Placebo	x	x	xx	x	xx	x	xx
Creatinine	Day 8	M2SR	x	x	xx	x	xx	x	xx
		Placebo	x	x	xx	x	xx	x	xx
	Max Severity Post Baseline	M2SR	x	x	xx	x	xx	x	xx
		Placebo	x	x	xx	x	xx	x	xx

Note: The “Max Post Baseline” rows indicate the maximum severity experienced by each subject at any time point post baseline, including unscheduled assessments.
N=Number of subjects in the Safety Population

Table 59: Chemistry Summary Statistics by Parameter, Time Point, and Study Group

[Implementation Note: For calculated fields (Mean, SD, Median), decimal place should be the format in which the data were collected + 1 extra place. For Min, Max, decimal place should be in the same format in which the data were collected.]

Laboratory Parameter (Units)	Time Point	Study Group	N	n	Value				Change from Baseline			
					Mean	Standard Deviation	Median	Min, Max	Mean	Standard Deviation	Median	Min, Max
Alanine Aminotransferase (U/L)	Screening	M2SR	x	x	xx.x	xx.x	xx.x	xx.x, xx.x	NA	NA	NA	NA
		Placebo	x	x	xx.x	xx.x	xx.x	xx.x, xx.x	NA	NA	NA	NA
	Day 8	M2SR	x	x	xx.x	xx.x	xx.x	xx.x, xx.x	xx.x	xx.x	xx.x	xx.x, xx.x
		Placebo	x	x	xx.x	xx.x	xx.x	xx.x, xx.x	xx.x	xx.x	xx.x	xx.x, xx.x
Aspartate Aminotransferase (U/L)	Screening	M2SR	x	x	xx.x	xx.x	xx.x	xx.x, xx.x	NA	NA	NA	NA
		Placebo	x	x	xx.x	xx.x	xx.x	xx.x, xx.x	NA	NA	NA	NA
	Day 8	M2SR	x	x	xx.x	xx.x	xx.x	xx.x, xx.x	xx.x	xx.x	xx.x	xx.x, xx.x
		Placebo	x	x	xx.x	xx.x	xx.x	xx.x, xx.x	xx.x	xx.x	xx.x	xx.x, xx.x
Creatinine (mg/dL)	Screening	M2SR	x	x	xx.x	xx.x	xx.x	xx.x, xx.x	NA	NA	NA	NA
		Placebo	x	x	xx.x	xx.x	xx.x	xx.x, xx.x	NA	NA	NA	NA
	Day 8	M2SR	x	x	xx.x	xx.x	xx.x	xx.x, xx.x	xx.x	xx.x	xx.x	xx.x, xx.x
		Placebo	x	x	xx.x	xx.x	xx.x	xx.x, xx.x	xx.x	xx.x	xx.x	xx.x, xx.x

Note: N= Number of subjects in the Safety Population; n= Number of subjects with results reported.

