## **8.2. Laboratory Evaluations**

### **8.2.1. Clinical Laboratory Evaluations**

Urine pregnancy tests will be performed locally by site laboratory at the Screening visit and within 24 hours prior to each study vaccination (Day 01 (Visit 01) and Day 92 (Visit 05) on all female adolescents of childbearing potential. Results must be negative and known prior to randomization on Day 1 and administration of each study vaccination to be eligible for participation in this study and receipt of each study vaccination.

- Clinical laboratory parameters to be evaluated at the Screening Visit (Visit 00) and on Day 08 (Visit 02) will include a White Blood Cell Count (WC), HGB, HCT (only at Visit 00), Platelet Count, ALT, AST, Serum Creatinine, Ferritin (at Visit 00), Prothrombin Time (PT) and Activated Partial Thromboplastin Time (aPTT). The results from the clinical safety laboratory parameters collected on Visit 00 will be available and reviewed prior to study

vaccination. Results of the HGB and HCT must be within normal limits, and Ferritin must be  $\geq 15$  ng/mL for enrollment. HGB will also be repeated at Day 22 and/or Day 57 if HGB is below the lower limit of normal or  $\geq 0.5$ g/dL below the baseline screening level at the day 8 follow up safety. HGB and Ferritin will be drawn at Day 113.

All other results can be and will serve as a Grade 1 or normal.

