### 9.2 Methods and Timing for Assessing, Recording, and Analyzing Safety Parameters

#### 9.2.1 Adverse Events

**Adverse Event (AE):** ICH E6 defines an AE as any untoward medical occurrence in a patient or clinical investigation subject administered a pharmaceutical product regardless of its causal relationship to the study treatment. An AE can therefore be any unfavorable and unintended sign (including an abnormal laboratory finding), symptom, or disease temporally associated with the

use of a medicinal (investigational) product. The occurrence of an AE may come to the attention of study personnel during study visits and interviews of a study recipient presenting for medical care, or upon review by a study monitor.

AEs, including solicited local (respiratory) and systemic (subjective and quantitative) reactions, not meeting the protocol-defined criteria for SAEs will be captured on the appropriate data collection form and eCRF. Information to be collected for unsolicited non-serious AEs includes event description, date of onset, licensed study physician's assessment of severity and relationship to study product and alternate etiology (if not related to study product) (assessed only by those with the training and authority to make a diagnosis and listed on the Form FDA 1572 as the site principal investigator or sub-investigator), date of resolution of the event, seriousness, and outcome. AEs occurring during the trial collection and reporting period will be documented appropriately regardless of relationship. AEs will be followed through resolution.

Any medical condition that is present at the time that the subject is screened will be considered as baseline and not reported as an AE. However, if the severity of any pre-existing medical condition increases, it will be recorded as an AE.

AEs must be graded for severity and assessed for relationship to study product (see definitions below). AEs characterized as intermittent require documentation of onset and duration of each episode. The start and stop date of each reported AE will be recorded on the appropriate data collection form and eCRF.

FDA defines an AE as any untoward medical occurrence associated with the use of a drug in humans, whether or not considered drug related.

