4.5.2. Safety Variables

Safety will be assessed by the frequency and severity of:

1. SAEs occurring from the time of the first study vaccination through 12 months after the first vaccination.
2. AESIs (wheezing, otitis media) and NOCMCs occurring from the time of the first study vaccination through 3 months after the first vaccination.
3. Solicited Adverse Events – reactogenicity events occurring from the time of experimental (first) study vaccination through 7 days after the first study vaccination.
4. Unsolicited Non-Serious Adverse Events –non-serious AEs occurring from the time of the first study vaccination through approximately 21 days after the first study vaccination.
5. Clinical safety laboratory AEs occurring at approximately 7 days after the first vaccination. Parameters to be evaluated include a WBC, HGB, Platelet Count, ALT, AST, Serum Creatinine, Ferritin level, PT and aPTT. HGB will also be repeated at Day 22 if there is a drop in HGB level from screen to Day 8 of > 0.5 g/dL or results are < lower limits of normal. If unable to collect at Day 22, collect at Day 57. If drawn at Day 22 and the results are still low, repeat at Day 57. If HGB results are still low at Day 57, no further PBMC collection will be done. HGB and Ferritin level will be drawn at Day 113. If the ferritin is < 15 ng/mL and/or the HGB is less than the lower limits of normal, will recommend follow-up with primary care provider for consideration of multivitamins with iron.

Grading scales for injection site and systemic solicited reactions, respiratory tract assessments, AESI, vital signs, and clinical laboratory parameters are provided in [Table 6](#), [Table 7](#), [Table 8](#), [Table 9](#), [Table 10](#), and [Table 11](#).

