9.6. Clinical Laboratory Evaluations

Clinical laboratory parameters to be evaluated at the Screening Visit (Visit 00) and on Day 08 (Visit 02) will include a White Blood Cell Count (WC), HGB, HCT (only at Visit 00), Platelet Count, ALT, AST, Serum Creatinine, Ferritin (at Visit 00), Prothrombin Time (PT) and Activated Partial Thromboplastin Time (aPTT). The grading scales for clinical laboratory evaluations are presented in Table 11 and Table 10. Clinical laboratory evaluations assessed on Day 1 prior to the first study vaccination will be considered as baseline.

Subjects with HGB below the lower limit of normal (LLN) at Day 8, or subjects who experience a drop of ≥ 0.5 g/dL between screening and Day 8, will have HGB re-drawn at Day 22. If HGB remains low (result is less than LLN or ≥ 0.5 g/dL lower than screening levels) at Day 22, or if HGB is not collected at Day 22, hemoglobin labs will be re-drawn at Day 57. Any subject where HGB results remain low at Day 57 will have no further PBMC collected. HGB and Ferritin will be drawn for all subjects at Day 113 (approximately 22 days post QIV vaccination). Ferritin results taken at Day 57 will be used for clinical decision making only – values will not be graded or included in summaries of clinical laboratory data, but will be included in the listings of hematology results (Listing 15).

The distribution of laboratory results by severity, study day and treatment group will be presented beginning with [Table 54](#), and continuing through [Table 65](#). Descriptive statistics including mean, standard deviation, median, minimum and maximum values and change from baseline by study day will be summarized for each parameter in [Table 59](#) and [Table 67](#). Box plots illustrating the change from baseline for each laboratory parameter will be presented in [Figure 56](#), [Figure 57](#), [Figure 58](#), [Figure 59](#), [Figure 60](#), [Figure 61](#), [Figure 62](#), and [Figure 63](#). Subject visits with abnormal laboratory results, Grade 1 severity or higher, will be presented in [Table 52](#) and [Table 53](#) for chemistry and hematology parameters, respectively. Abnormal results will be summarized by visit and study arm in [Table 58](#) and [Table 66](#) for chemistry and hematology parameters, respectively.

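### For tests other than HGB, the laboratory grade tables do not separate a Grade 1 value carried over from screening from a new one, and no shift or treatment-emergent table by arm is planned

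*SAP*

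**What the plan says.** SAP 4.5.2 lists as its own safety variable "Clinical safety laboratory AEs occurring at approximately 7 days after the first vaccination", apart from unsolicited non-serious AEs. Protocol 9.2.1 includes abnormal laboratory findings in its definition of an AE. It says that a medical condition present at screening "will be considered as baseline and not reported as an AE", but that "if the severity of any pre-existing medical condition increases, it will be recorded as an AE".

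On entry values, Protocol 8.2.1 states "Results of the HGB and HCT must be within normal limits", sets a minimum for ferritin, and then adds "All other results can be and will serve as a Grade 1 or normal". The last sentence is garbled. Its most natural reading is that every other test may be normal or Grade 1 at screening.

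SAP Tables 54-57 (chemistry) and 60-65 (hematology) show the grade distribution by arm at screening and Day 8, with Days 22 and 57 added in Tables 60 and 61. They end with a row defined as "the maximum severity experienced by each subject at any time point post baseline, including unscheduled assessments". Tables 58 and 66 carry a title beginning "Abnormal Laboratory Results Related to Study Treatment by Parameter", yet SAP 9.6 introduces them with "Abnormal results will be summarized by visit and study arm in" and no limit on relationship.

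SAP 9.6 also sets the laboratory baseline at Day 1 before vaccination. SAP 3.3 uses the last value before the first dose, and the table shells use Screening.

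**The concern.** If a finding present at entry is an AE only when it worsens, a count of laboratory AEs needs each child's post-dose grade set against that child's own pre-dose grade. The Day 8 and maximum-severity rows do not do this. A child with Grade 1 ALT at screening and Grade 1 ALT at Day 8 appears as a Grade 1 post-dose result, in the same cell as a child whose ALT was normal at entry.

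Safety is the primary objective, and each arm has about 25 children. A reader will want to know how many children in each arm had a laboratory value that became abnormal or rose in grade after dosing. The planned grade tables do not give that number for tests other than HGB. Tables 58 and 66 would not supply it either if their titles are followed, because they would then depend on a causality judgment.

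**Working it through.** The plan states no figure on this point, so there is none to reproduce. The check compares definitions and then shows how far they can matter.

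**1. Which tests can carry a grade over from screening?**

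For HGB, inclusion criterion 12 requires at least 11.5 g/dL. The top of Grade 1 (Protocol 9.2.5, SAP Table 10) is 10.4 for ages 9-12, 10.9 for males 13 and over, and 10.4 for females 13 and over. The gaps are:
- ages 9-12: 11.5 - 10.4 = 1.1 g/dL
- males 13 and over: 11.5 - 10.9 = 0.6 g/dL
- females 13 and over: 11.5 - 10.4 = 1.1 g/dL

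A child who meets the current criterion cannot be graded for HGB at screening, so every post-dose grade in Table 61 is new. A possible exception is any of the 19 children enrolled in 2018 who entered before the amendment described in SAP 4.3; the documents do not give the earlier limit.

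ALT, AST, creatinine, WBC, platelets, PT and aPTT have no such gap. Table 60 pools all hematology tests, so carry-over can enter it through WBC, platelets, PT and aPTT.

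**2. Which grades?** If entry allows only normal or Grade 1, any post-dose Grade 2 or 3 is a worsening. Only the Grade 1 column is mixed. Grades 2-3 for creatinine are also partly defined against the child's own baseline; Grade 1 is not.

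**3. Do the screening rows resolve it?** No, because they are arm totals. Let *a* of *n* children be graded at screening and *b* of *n* at Day 8. The number newly graded can lie anywhere from max(0, *b* - *a*) to min(*b*, *n* - *a*). With *n* = 25 and *a* = *b* = 3, it runs from 0 to 3. This step needs no assumed rate.

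**4. Illustration of size.** The documents give no rates, so the following are assumptions for a given table: *q* = share Grade 1 at screening, *s* = share of those still Grade 1 at Day 8, *e* = new-onset rate among the rest.

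- Carried-over children per arm = 25 × *q* × *s*. Low end: 25 × 0.05 × 0.5 = 0.6. High end: 25 × 0.20 × 0.8 = 4.0.
- Count shown in the table = 25 × [*q*·*s* + (1 - *q*)·*e*]; new count = 25 × (1 - *q*)·*e*.

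| *q* | *s* | *e* | Shown | New |
|---|---|---|---|---|
| 0 | any | 0.04 | 1.0 | 1.0 |
| 0 | any | 0.10 | 2.5 | 2.5 |
| 0.10 | 0.5 | 0.04 | 2.15 | 0.90 |
| 0.10 | 1.0 | 0.10 | 4.75 | 2.25 |

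If no child is graded at screening, the two counts are the same.

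**5. Is the number elsewhere?** Tables 59 and 67 and Figures 56-63 give change from baseline on the continuous scale, not the number of children whose grade rose. Tables 52-53 and Listings 14-15 give results by child with grades, but are not summaries by arm. Table 38 has no laboratory row. Tables 45-47 cover all reported AEs by arm, but neither document says whether a graded laboratory result is entered as an AE.

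**6. Which baseline?** The Day 1 baseline in SAP 9.6 cannot be applied. Protocol Table 2 and the SAP schedule show no safety laboratory draw at Visit 01. The last pre-dose value is therefore the screening value.

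**The case against.** The strongest reply is that the information is largely available. Each grade table has a screening row by arm, continuous change from baseline is summarised by arm, and the listings show each child's graded result at each time point. With about 50 children, shifts could be read by hand. Randomisation balances carried-over grades between arms in expectation, and the study is descriptive. The protocol's worsening rule speaks of a medical condition and is not expressly applied to laboratory grades, while entry at Grade 1 rests on one unclear sentence.

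Much of this stands. Carry-over inflates both arms and adds noise; it is not an expected bias in the difference. The premise about entry grades is a reading, not a stated rule. But a listing that the reader must tally is not a planned summary, and step 3 shows that arm totals cannot replace within-child comparison.

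A reader might also infer that no table at all gives laboratory AEs by arm. The documents do not support that: laboratory findings entered as AEs would appear in Tables 45-47, and the plan is silent rather than negative on this. Nor do they support the inference that only related results are counted, because Tables 54-57 and 60-65 have no such limit. The restriction in Tables 58 and 66 is a conflict between title and text.

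**Conclusion.** The point holds for laboratory tests other than HGB, and for the pooled hematology table through those tests. Post-dose Grade 1 counts can mix persisting with new abnormalities, and the plan has no shift or treatment-emergent summary by arm to separate them. It depends on reading Protocol 8.2.1 as admitting Grade 1 screening values and on applying the worsening rule in Protocol 9.2.1 to laboratory grades.

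The size is unknown. The 0.6 to 4 children per arm is an illustration from assumed rates and need not be reached in any one table.

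It would be tempting to extend this to HGB, the parameter behind the amendment. The entry limits rule that out, apart from possible pre-amendment children. The two mismatches in SAP 9.6 (the scope of Tables 58 and 66, and the Day 1 baseline) need no assumption and should be reconciled in any case.

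**What to change.** 1. In SAP 9.6, define a treatment-emergent laboratory abnormality as a post-dose grade higher than the last pre-dose (screening) grade. Replace the Day 1 baseline statement so that it agrees with SAP 3.3 and the schedule. The baseline-relative creatinine grades need the same definition.
2. Add treatment-emergent rows by arm, or a screening-to-post-dose shift table, to Tables 54-57 and 60-65. Keep the existing all-values rows. Replacing them would set raw prevalence at screening beside emergent counts after dosing in one table, and would lose the post-dose grade distribution.
3. Make Tables 58 and 66 show all treatment-emergent abnormalities with a sub-row for those judged related, and retitle them to match SAP 9.6.
4. State whether graded laboratory results also enter Tables 45-47.

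The cost is SAP wording, one derivation flag from data already collected, and a few more table rows. This is a cheap improvement with a small downside in table length.
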